## 11. CORRELATIVE SCIENCE

### 11.1 Rationale

One of the major shortcomings of immunotherapy trials has been the lack of in depth correlative studies to help identify the mechanism of action of these therapies, identify biomarkers of response, and provide a foundation for further improving these approaches. To address this we plan to perform in depth immunological analysis of patient blood and tumor samples. Pre- and post-treatment blood and tumor biopsies (when available) will be obtained as outlined in the study calendar. Briefly, blood and tumor samples will be collected pre-treatment on Day 1 and again at Day 15. Blood samples will also be collected at 60 day check-up visits. Optional blood and tumor biopsies can be obtained at progression. Participation in the correlative studies is mandatory unless waived by the study principal investigator due to safety concerns or other reasons. Archival tumor blocks will also be collected when available. We will evaluate immunologic changes systemically and in the tumor and tumor microenvironment within patient's pre to post therapy and across the cohort of patients to identify predictive biomarkers and elucidate the mechanistic immunologic effects of therapy. For further details, refer to Appendix 4 and Table 10 in Section 10.3. Correlative studies will include (in order of priority):

#### Blood

- FACS for quantification, immunophenotyping, and functional assessment of PBMCs

- qPCR (quantitative polymerase chain reaction) evaluation of immune gene signatures including: cytokines, T-cell activation markers, immunosuppressive enzymes and molecules (IDO [indoleamine-pyrrole 2,3-dioxygenase], arginase, CTLA-4, PD-1/PD-L1), macrophage polarization, etc.
- Nanostring gene panel
- Whole exome sequencing
- Evaluation of systemic plasma tryptophan to kynurenine ratios
- Luminex evaluation of plasma for systemic cytokine / chemokine signatures
- T-cell receptor (TCR) deep sequencing to determine clonal expansion of T-cells in the systemic circulation
- Other studies as deemed feasible and informative by the principal investigators

#### Tissue

- IHC to determine expression of markers including PD-1, PD-L1, CD8, CD4, IDO and FOXP3
- qPCR evaluation of the tumor microenvironment gene signatures including: cytokines, T-cell activation markers, immunosuppressive enzymes and molecules (IDO, arginase, CTLA4, PD-1/PD-L1), macrophage polarization, etc.
- Nanostring gene panel on FFPE tissues or snap frozen tissues
- Whole exome sequencing
- Other studies as deemed feasible and informative by the principal investigators

#### Stool

- Stool microbiome analysis

A comprehensive analysis of tumor, blood, and stool samples will provide valuable insight into potential biomarkers and into the mechanism of action of our combined therapy.

### 11.2 Correlative Study Design and Methodology

We have extensive expertise in all of the techniques described at the UC Davis Laboratory of Tumor Immunology. Blood samples will be separated into PBMCs and plasma and stored at -80 for batched analysis. PBMCs will be stained for FACS analysis using well characterized antibodies against markers such as CD45, CD3, CD4, CD8, FOXP3, Granzyme B, Interferon gamma, tumor necrosis factor (TNF) alpha, PD-1, etc. Results will be analyzed using a BD Fortessa multi-color flow cytometer and Flowjo software. An aliquot of PBMCs will also be set aside for RNA isolation and batched analysis of gene expression. mRNA (messenger ribonucleic acid) will be extracted using RNeasy kits (Qiagen) and reverse transcribed to cDNA. Cellular RNA will be analyzed by qRT-PCR (real-time reverse transcription-polymerase chain reaction) using verified primers to investigate the expression of genes

including IDO, arginase, iNOS (inducible Nitric oxide synthases), CTLA-4, PD-1, PD-L1 and others. RNA will also be analyzed using a Nanostring gene panel. To determine if certain clones of T cells are preferentially expanding after therapy, an aliquot of PBMCs will also be used for TCR deep sequencing. Plasma will be evaluated for systemic cytokine and chemokine signatures using Luminex technology. Markers will include IL-2, IL-6, IL-10, IL-12p70, GM-CSF (granulocyte-macrophage colony-stimulating factor), TNF alpha, IFN (interferon) gamma, CXCL10 (C-X-C motif chemokine 10), RANTES (regulated on activation, normal T cell expressed and secreted), MIP1 (Macrophage Inflammatory Protein) alpha, MIP1 beta, TGF-beta and others. Tissue biopsies will be formalin fixed and paraffin embedded using standard protocols. Tissue will be analyzed by IHC staining for PD-1, PD-L1, FOXP3, CD8, and CD4 markers. If sufficient biopsy material is available then a tissue sample will be stored in RNA later for batched analysis by qPCR / Nanostring as described above. Whole exome sequencing will also be performed on tumor tissue and compared to the peripheral blood as a normal tissue control to determine the mutational load of the tumor. Pre-treatment stool samples will be collected to analyze the gut microbiome.

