##### 4.1 Inclusion Criteria

1. Adults  $\geq 18$  years of age with histologically proven solid malignancy, high-grade lymphoma or low-grade lymphoma.
2. Patients with incurable, advanced or metastatic disease refractory to at least one previous line of therapy.
3. ECOG (Eastern Cooperative Oncology Group) performance status score of 0 – 2 (Appendix 1).
4. Presence of a candidate treatment lesion (subcutaneous, nodal, or visceral) accessible and safe for radiotherapy and serial intralesional injections as specified by the protocol.
5. Presence of at least one target lesion (distinct from treatment lesion and outside of treatment lesion radiation field) evaluable for response by irRECIST.
6. 14 day wash-out period from any previous chemotherapy, targeted therapy or radiotherapy, 21 day washout period from previous immunotherapy.
7. Life expectancy  $\geq 6$  months.
8. Adequate hematologic and end organ function, defined by the following laboratory results obtained within 14 days of the first study treatment:
  - o ANC  $> 1500$  cells/uL; WBC count  $> 2500$ /uL; Platelet count  $> 50,000$ /uL; Hemoglobin  $> 9$  g/dL
9. Liver function tests meeting one of the following criteria:
  - a. AST and ALT  $< 2.5$  x ULN with alkaline phosphatase  $\leq 2.5$  x ULN OR

- b. AST and ALT  $\leq 1.5 \times$  ULN, with alkaline phosphatase  $> 2.5 \times$  ULN
  - c. Serum bilirubin  $\leq 1.0 \times$  ULN. Direct bili  $\leq 40\%$  if total bili  $>$  ULN in patients with Gilbert's syndrome.
10. INR and aPTT  $< 1.5 \times$  ULN.
  11. Serum Cr  $\leq 1.5 \times$  ULN or CrCl  $\geq 50$  ml/min.
  12. No active auto-immune disease and not on therapy for auto-immune disease. Patients with a history of autoimmune-related hypothyroidism on a stable dose of thyroid replacement hormone are eligible. Patients who have adrenal insufficiency and hypophysitis from prior immunotherapy if they are on stable medical replacement doses are eligible.
  13. No other active malignancy.
  14. Patients with controlled Type 1 diabetes mellitus on a stable insulin regimen are eligible.
  15. For female patients of childbearing potential and male patients with partners of childbearing potential agreement (by patient and/or partner) to use highly effective form(s) of contraception (i.e., one that results in a low failure rate [ $<1\%$  per year] when used consistently and correctly) and to continue its use for 6 months after trial completion.
  16. Signed informed consent.

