  17. At least 9 months from stem cell transplant with no active graft versus host disease.
  18. Ability to comply with the protocol.

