## **12. DATA AND STATISTICAL ANALYSIS PLAN**

### **12.1 Sample Size**

For the dose escalation phase a traditional 3 + 3 design will be used with the goal of determining the MTD through DLT assessment. Per design each cohort will consist of 3-6 patients. The number of patients will depend on the occurrence of DLT (Table 1). We estimate a minimum of 6 patients and a maximum of 18 patients (6 patients/cohort) would be enrolled. Once the MTD is determined patients will be enrolled into either a lymphoma or a solid tumor phase 2 cohort which will generate preliminary efficacy data to determine if the treatment regimen should be considered for a randomized study. Patients treated at the MTD during the phase I will also be used as part of the phase II cohorts to minimize patient numbers. For the solid tumor cohort (cohort 1) we have set a threshold DCR response rate of 20% by irRECIST as worthy of further study and this cohort will enroll 16-30 evaluable patients. In the first stage 16 patients (n1) will be enrolled and greater than 1 response (r1) is required for the trial to proceed. In the second stage an additional 14 patients will be enrolled for a total of 30 patients (nTot) and greater than 3 responses (rTot) are required for the therapy to be deemed worthy of further study in a randomized trial. For the lymphoma cohort (cohort 2) we have set a threshold DCR response rate of 30% by irRECIST as worthy of further study and this cohort will enroll 7-14 evaluable patients. In the first stage 7 patients (n1) will be enrolled and greater than 0 responses (r1) are required for the trial to proceed. In the second stage an additional 7 patients will be enrolled for a total of 14 patients (nTot) and greater than 2 responses (rTot) are required for the therapy to be deemed worthy of further study in a randomized trial. Patients who are not evaluable for treatment efficacy (see section 12.4) will

not be included in the Simon two-stage analysis and will be replaced by additional patient enrollment to ensure a full cohort of evaluable patients.

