The primary endpoint of this study is to determine the MTD of epacadostat when combined with SD-101 and radiotherapy. In the two phase II expansion cohorts we will further assess safety and efficacy of this regimen at the proposed MTD. The expansion will employ a Simon two-stage design to determine if the treatment efficacy warrants further investigation in a randomized study. The sample size was determined by the dose-escalation design combined with a Simon two-stage design for our required efficacy endpoints. When the true response rates are at their respective thresholds both two-stage designs have 80% to reject at the 0.05 level (1-sided) the null hypothesis that the DCR response rate is an unacceptably low 5%. Since patients treated at the MTD will be included in the phase II expansion analysis a maximum of 56 evaluable patients will be enrolled.

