#### Blood

- 1) Flow Cytometry quantification, immunophenotyping, and activation / functional assessment of tumor infiltrating immune cells including myeloid-derived suppressor cells (MDSC), regulatory T (Treg) cells, T/B/NK cell immunophenotyping and activated T cells
- 2) RNA extraction for qPCR and Nanostring analysis
- 3) Whole exome sequencing (WES) as a normal tissue control to identify putative neo-antigens
- 4) Evaluation of systemic plasma tryptophan to kynurenine ratios
- 5) Peripheral blood cytokine / chemokine profiling by Luminex
- 6) T-cell receptor (TCR) deep sequencing to determine clonal expansion of T-cells in the systemic circulation
- 7) Other studies as deemed feasible and informative by the principal investigators

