### *1.2.4 Snap frozen for DNA extraction*

This specimen will be collected from the pre-treatment blood draw only. After counting, PBS washed PBMCs should be spun down at approximately 1,000-1,500 rpm (400 x g) for 10 minutes. The cell pellet should be snap frozen in liquid nitrogen and stored at -70 to -80°C. In a batched manner tubes should be shipped overnight on dry ice to UC Davis at the indicated address.

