### 2.3 Tumor biopsy analysis

FFPE tissue biopsy blocks will be collected and stored at UC Davis. Tissues will be sectioned, prepared, and mounted for IHC/IF using standard procedures. When possible, IHC/IF should be performed within two weeks of slide sectioning. Biopsy samples will be stained by multiplex IHC/IF at UC Davis or collaborating laboratories to immunologically profile the tumor microenvironment. Markers examined will include CD3, CD8, CD4, FoxP3, Ki-67, PD-1 and PD-L1.

Tissue in RNA later will be stored at UC Davis for batched analysis. Samples will be thawed and RNA will be extracted. The transcriptome will be analyzed using a nanostring 770 gene panel. Targeted RT-PCR will be used to validate genes of interest. RNAseq data will also be used in conjunction with PBMC WES to identify mutational load and putative neoantigens.

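### Pre-treatment PBMC DNA is the only normal control for mutational load, but eligibility admits patients in whom it fails: allogeneic recipients with donor-derived blood, and possibly lymphoma patients with circulating tumor cells

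*Combined protocol and SAP*

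**What the plan says.** **The control.** Section 11.2 sets the comparison used to determine mutational load: "Whole exome sequencing will also be performed on tumor tissue and compared to the peripheral blood as a normal tissue control". Appendix 4 lists the same assay among the blood studies: "Whole exome sequencing (WES) as a normal tissue control to identify putative neo-antigens". Its section 2.3 names the cell fraction: "RNAseq data will also be used in conjunction with PBMC WES to identify mutational load and putative neoantigens". Section 1.2.4 of that appendix fixes the timing of the DNA aliquot: "This specimen will be collected from the pre-treatment blood draw only".

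**Other samples.** Appendix 4 collects blood, tumor biopsy and stool, with stool reserved for microbiome sequencing. Section 11.1 adds archival tumor blocks when available. No buccal, skin or other non-hematopoietic germline sample is listed.

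**Who may enter.** Section 4.1, criterion 1, admits adults with "histologically proven solid malignancy, high-grade lymphoma or low-grade lymphoma". Criterion 17 reads: "At least 9 months from stem cell transplant with no active graft versus host disease". Neither 4.1 nor 4.2 restricts transplant type or excludes blood or marrow involvement. For the lymphoma cohort, section 12.1 says "this cohort will enroll 7-14 evaluable patients".

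**How the result is used.** Objective 1.3.3 includes mutational load. Objective 1.3.5 seeks biomarkers of response from the data of 1.3.3 and related objectives. Section 12.6 describes correlative markers across the cohorts and relates them to response and time to event by regression. It labels them exploratory.

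**The concern.** A matched normal is useful only if it carries the patient's own inherited genome and is essentially free of tumor. Two eligible groups can break one of these conditions.

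- **Donor-derived blood.** The graft-versus-host condition in criterion 17 has a purpose only if allogeneic recipients can enter. If their blood cells come from the donor, the tumor is compared with another person's genome.
- **Circulating lymphoma.** PBMCs are the fraction that holds lymphocytes, and the aliquot is drawn before treatment, while disease is active. If lymphoma cells circulate, the control contains tumor.

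The first error inflates load and the second deflates it. An analysis that pools patients would mix the two with valid values, and nothing in the plan would flag the affected patients. At stake is the interpretability of mutational load and neo-antigens as candidate biomarkers.

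**Working it through.** The plan gives no figure for mutational load, sequencing depth, variant-calling rule or number of transplant recipients, so there is nothing to reproduce. The check sets the sections side by side, then adds arithmetic on labelled assumptions.

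**Step 1: which patients have a valid control under the plan as written**

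| Patient | Source of PBMC DNA | Effect on load |
|---|---|---|
| Solid tumor, no allogeneic transplant | Own germline | None |
| Autologous recipient, no circulating lymphoma | Own germline | None |
| Allogeneic recipient, donor-derived blood (either cohort) | Donor germline | Recipient variants absent in the donor counted as somatic: too high |
| Lymphoma, no circulating disease, own blood | Own germline | None |
| Lymphoma, circulating tumor cells | Own germline plus tumor | True mutations can be removed: too low |

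No section provides a check for either failing row or an exception for it.

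**Step 2: size of the group at possible risk.** The phase 2 range is 16 to 30 solid tumor and 7 to 14 lymphoma patients (schema and 12.1). Lymphoma is therefore 7/(16+7) = 7/23 = 30% at the minimum and 14/(30+14) = 14/44 = 32% at the maximum. This bounds the patients in whom circulating disease could arise; it is not the number affected. The number of allogeneic recipients is not given. Section 2.5 mentions SD-101 given to 5 patients with non-Hodgkin lymphoma progressing after allogeneic transplant, so such patients are plausible candidates.

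**Step 3: overcounting, in relative terms.** Assume every patient has true load m and one allogeneic recipient among n = 14 has g false variants added. The cohort mean relative to the truth is 1 + (g/m)/14.

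- g = m: 1 + 1/14 = 1.07
- g = 5m: 1 + 5/14 = 1.36
- g = 50m: 1 + 50/14 = 4.57

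The documents do not give g/m. These lines show how the error scales; they do not estimate it.

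**Step 4: undercounting.** Let c be the fraction of PBMCs that are tumor. A clonal heterozygous variant then appears in the control at allele fraction c/2. Suppose the variant is removed when at least k alternate reads are seen at depth D, with independent reads. The probability of removal is P(X ≥ k), with X ~ Binomial(D, c/2). D, k and c are assumptions.

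| D, k | c = 0 | c = 1% | c = 5% | c = 10% | c = 20% |
|---|---|---|---|---|---|
| 60, 3 | 0 | 0.003 | 0.19 | 0.58 | 0.95 |
| 100, 3 | 0 | 0.014 | 0.46 | 0.88 | 0.998 |
| 60, 2 | 0 | 0.037 | 0.44 | 0.81 | 0.99 |
| 100, 2 | 0 | 0.090 | 0.72 | 0.96 | 1.00 |

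The loss is nil without circulating tumor, small at 1%, partial at 5% and close to complete at 20%.

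**The case against.** **The stronger reading fails.** A reader might infer that mutational load is wrong in every transplant recipient and every lymphoma patient. The documents do not support that. Autologous recipients carry their own germline, and a lymphoma patient without circulating disease has a sound blood control. It may be that no enrolled patient is affected.

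**The size is not established.** No caller, depth or population-variant filter is specified, and a filter could remove many of the false variants in an allogeneic recipient. Section 11.2 describes tumor exome sequencing, Appendix 4 describes tumor RNA sequencing read against PBMC exome data, and Table 10 names both, so exome-wide counts may not carry over. This stands, and no absolute figure is claimed here. The control is PBMC DNA in either case, so the direction of each error is unchanged.

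**Influence on the regression.** A reader might also infer that one aberrant value would decide the biomarker model. Section 12.6 specifies no cohort-specific model and no scale or transformation for load, so this cannot be shown.

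**Existing safeguards.** Section 11.1 lets the principal investigator waive correlative participation for safety or other reasons. That is discretionary and not tied to the validity of the control, so it does not answer the point.

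**Exploratory status.** These endpoints are labelled hypothesis-generating, and this limits the consequence. It does not make an invalid comparator valid.

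**Conclusion.** The concern holds in a limited form. Followed as written, the plan uses an invalid normal control for any allogeneic recipient with donor-derived blood, and a possibly invalid one for any lymphoma patient with circulating tumor cells. The errors run in opposite directions. The first conclusion rests on reading the graft-versus-host clause in criterion 17 as admitting allogeneic recipients; the second depends on tumor cells being present in the baseline blood.

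The number affected is unknown and may be zero, and the size of the error cannot be computed from the documents. The consequence is confined to the exploratory mutational-load and neo-antigen work under objectives 1.3.3 and 1.3.5 and section 12.6. MTD, safety, disease control rate, abscopal response rate and the Simon two-stage decisions are untouched. The change is still worth making because the allogeneic error is foreseeable and can be avoided at almost no cost.

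**What to change.** In section 11.2 and Appendix 4:

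1. Exclude patients with a prior allogeneic transplant from the mutational-load and neo-antigen analyses. Identify them from the medical history already taken at screening, and make sure that the transplant type is recorded.
2. Report these measures for lymphoma separately from solid tumors.
3. Within lymphoma, add a sensitivity analysis that omits patients with known or suspected blood involvement, using the baseline differential and the planned PBMC flow cytometry. Present it as a sensitivity analysis only. The listed flow markers include CD19 and CD20 but name no light-chain marker, and neither test is shown to detect circulating tumor at the 5 to 10% level.
4. Report the number of patients excluded and why.
5. Do not substitute archival block tissue as the normal unless it is confirmed to be both non-hematopoietic and uninvolved. Nodal tissue taken after a transplant could repeat the same error.

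The cost is wording in the correlative plan and the loss of a few patients from one exploratory analysis. No new procedure or sample is needed.

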## **12. DATA AND STATISTICAL ANALYSIS PLAN**

### **12.1 Sample Size**

For the dose escalation phase a traditional 3 + 3 design will be used with the goal of determining the MTD through DLT assessment. Per design each cohort will consist of 3-6 patients. The number of patients will depend on the occurrence of DLT (Table 1). We estimate a minimum of 6 patients and a maximum of 18 patients (6 patients/cohort) would be enrolled. Once the MTD is determined patients will be enrolled into either a lymphoma or a solid tumor phase 2 cohort which will generate preliminary efficacy data to determine if the treatment regimen should be considered for a randomized study. Patients treated at the MTD during the phase I will also be used as part of the phase II cohorts to minimize patient numbers. For the solid tumor cohort (cohort 1) we have set a threshold DCR response rate of 20% by irRECIST as worthy of further study and this cohort will enroll 16-30 evaluable patients. In the first stage 16 patients (n1) will be enrolled and greater than 1 response (r1) is required for the trial to proceed. In the second stage an additional 14 patients will be enrolled for a total of 30 patients (nTot) and greater than 3 responses (rTot) are required for the therapy to be deemed worthy of further study in a randomized trial. For the lymphoma cohort (cohort 2) we have set a threshold DCR response rate of 30% by irRECIST as worthy of further study and this cohort will enroll 7-14 evaluable patients. In the first stage 7 patients (n1) will be enrolled and greater than 0 responses (r1) are required for the trial to proceed. In the second stage an additional 7 patients will be enrolled for a total of 14 patients (nTot) and greater than 2 responses (rTot) are required for the therapy to be deemed worthy of further study in a randomized trial. Patients who are not evaluable for treatment efficacy (see section 12.4) will

not be included in the Simon two-stage analysis and will be replaced by additional patient enrollment to ensure a full cohort of evaluable patients.

The primary endpoint of this study is to determine the MTD of epacadostat when combined with SD-101 and radiotherapy. In the two phase II expansion cohorts we will further assess safety and efficacy of this regimen at the proposed MTD. The expansion will employ a Simon two-stage design to determine if the treatment efficacy warrants further investigation in a randomized study. The sample size was determined by the dose-escalation design combined with a Simon two-stage design for our required efficacy endpoints. When the true response rates are at their respective thresholds both two-stage designs have 80% to reject at the 0.05 level (1-sided) the null hypothesis that the DCR response rate is an unacceptably low 5%. Since patients treated at the MTD will be included in the phase II expansion analysis a maximum of 56 evaluable patients will be enrolled.

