**SCHEMA**

- General Enrollment Criteria**
- Advanced refractory solid tumors or lymphoma
  - Age ≥18
  - 14 day treatment washout period
  - At least one candidate treatment lesion (subcutaneous, nodal, or visceral)
    - Accessible for RT
    - Accessible and safe for repeat intralesional injections
  - At least one candidate target lesion, outside of the RT field evaluable for response per irRECIST
  - Adequate hematologic and end organ function
  - No active autoimmune disease
  - Patients with previous checkpoint blockade therapy are eligible

- Concurrent RT (Days 1-5)**
- Cohort 1 (solid tumors): (8 Gy x 3) or (4 Gy x 5)
  - Cohort 2 (lymphoma): (8 Gy x 3) or (4 Gy x 5) or (2 Gy x 2)
- +
- Intralesional SD-101 (Day 1, 8, 15, 22, 29)**  
4 mg injection into RT treatment lesion
- +
- Epacadostat**  
50-300 mg PO bid

Phase I Dose Finding	
3+3 Design: (3-6 patients per dose level, 6-18 patients total)	
Dose level -3:	50 mg PO bid
Dose level -2:	100 mg PO bid
Dose level -1:	200 mg PO bid
Dose level 1:	300 mg PO bid

Phase II Expansion Cohorts	
Simon Two-Stage Design	
Cohort 1:	Solid tumor (16-30 patients) P0=0.05, p1=0.20, r1=1, n1=16, rTot=3, nTot=30, α=0.05, power=0.8
Cohort 2:	Lymphoma (7-14 patients) P0=0.05, p1=0.3, r1=0, n1=7, rTot=2, nTot=14, α=0.05, power=0.8

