### 3. STUDY DESIGN

This is a phase I/II study that will use a standard 3 + 3 design followed by a Simon-two stage patient expansion as illustrated in the schema. For the phase I portion the primary endpoint is to determine the maximum tolerated dose (MTD). For the phase II portion the primary endpoint is safety and toxicity. Safety and toxicity will be evaluated using CTCAE v4.03. The secondary endpoint and the endpoint used for the Simon-two stage design is the disease control rate (DCR) defined as complete response + partial response + stable disease (CD+PR+SD). This endpoint is being used because several studies have demonstrated that patients without response to immunotherapy can still have long term disease stability which is of clinical benefit. Determining treatment tolerability (as defined in section 6.6) is also a secondary endpoint. Exploratory endpoints include objective response rate (ORR), progression free survival (PFS), overall survival (OS), and correlative studies.

Up to four dose levels of epacadostat will be evaluated: 50 mg bid, 100 mg bid, 200 mg bid and 300 mg bid. These 4 dose levels were selected based on the clinical data described above. We have chosen 300 mg bid as the starting dose level given the existing safety data for this dose and the safe use of this dose in use with other immunotherapy combinations. There is a -1, -2 and -3 dose level. If dose level -3 is not tolerated the study will be halted and modified after discussion with principal investigators and study sponsors. Epacadostat will be administered orally twice daily until disease progression. The expansion phase will be conducted using the MTD defined as the highest dose at which no more than one of six patients develops a DLT or Dose Level 1 if the MTD is not reached.

Radiotherapy will be delivered to the treatment lesion during the first week of ERS therapy using one of the following three standard-of-care palliative fractionation regimens: 8 Gy x 3 fractions, 4 Gy x 5 fractions, or 2 Gy x 2 fractions (cohort 2 only). Fractions may be delivered on consecutive or every other day but must be completed during week 1. The treatment lesion may be in a previously irradiated field as long as previous radiotherapy to that field was delivered > 6 months ago and re-irradiation is deemed safe.

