**Table 1. Dose De-Escalation Rules**

Number of Patients with DLT at a Given Dose Level	De-Escalation Decision Rule
0 or 1 out of 3	Enter 3 additional patients at the dose level.
$\geq 2$ out of 3 or 6	De-escalate the dose to the next lower level and accrue 3 patients.
$< 2$ out of 6 at the highest dose level	This is the recommended phase 2 dose.

DLT=dose limiting toxicity

Patients will be monitored weekly during a 30-day DLT period and every 30 days thereafter or more frequently if needed. All patients on active treatment will be discussed at weekly conferences of the trial investigators. Per Cancer Center guidelines, a trial cannot proceed to the next dose level until a DLT meeting is conducted to comprehensively review all toxicity data and approve the dose escalation. Preliminary efficacy as determined by ARR, ORR, DCR, OS and DFS will be assessed every 60 days. The patient will remain on protocol

treatment until progression as determined by irRECIST, treatment is no longer tolerated, or the patient has completed 12 months of treatment. Patients on active treatment at 12 months may continue to receive epacadostat if they are tolerating therapy and are free from disease progression by irRECIST criteria. If patients have an objective response and stop treatment after 12 months and then have PD, they can be considered for re-treatment at the discretion of the study PI. After study completion PFS, OS and long-term toxicity data will continue to be collected every 3 months during routine standard of care visits.

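### The stated maxima of 18 phase I patients and 56 evaluable patients count three dose levels; the design has four, which gives 24 and 62.

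*Combined protocol and SAP*

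**What the plan says.** Section 12.1 sizes the dose-finding phase in one sentence: "We estimate a minimum of 6 patients and a maximum of 18 patients (6 patients/cohort) would be enrolled". The Schema repeats the range: "3+3 Design: (3-6 patients per dose level, 6-18 patients total". For the whole trial, section 12.1 says that "a maximum of 56 evaluable patients will be enrolled", after explaining that phase I patients treated at the MTD also count in the expansion cohorts. Those cohorts have maxima of 30 (solid tumor) and 14 (lymphoma).

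The number of dose levels is given elsewhere. Section 3 says: "Up to four dose levels of epacadostat will be evaluated: 50 mg bid, 100 mg bid, 200 mg bid and 300 mg bid", and "There is a -1, -2 and -3 dose level", in addition to the starting level 1. The Schema and Table 5 (section 6.6) list the same four levels.

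Table 1 sets the accrual rule. After 0 or 1 DLT in the first 3 patients: "Enter 3 additional patients at the dose level". After 2 or more DLTs out of 3 or out of 6: "De-escalate the dose to the next lower level and accrue 3 patients". For the lowest level, section 3 adds: "If dose level -3 is not tolerated the study will be halted and modified after discussion with principal investigators and study sponsors".

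**The concern.** At six patients per level, 18 patients is three levels, and the design has four. The overall figure of 56 appears to be built on the same three-level count. If so, neither number is a maximum, because a trial that follows Table 1 exactly could pass both. These are the enrolment ceilings the protocol states. If accrual reached one of them part-way through the fourth level or during stage 2, the dosing or Simon rules would call for more patients than the stated ceiling allows. That conflict would arise only when toxicity had been worse than expected.

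**Working it through.** **Inputs**

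- Dose levels: 4 (Schema, section 3, Table 5).
- Patients per level under Table 1: 3 then de-escalate, 6 then de-escalate, or 6 and declared the MTD.
- Patients at the MTD who also count in phase II: 6 (sections 3 and 12.1).
- Cohort maxima: 30 + 14 = 44 (section 12.1).

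**Reproducing the plan's figures (three levels)**

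- Phase I: 3 x 6 = 18, as stated.
- Overall: 18 - 6 + 30 + 14 = 56, as stated.

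**Same formulas with four levels**

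- Phase I: 4 x 6 = 24.
- Overall: 24 - 6 + 30 + 14 = 62.

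Enumerating every path that Table 1 allows gives the same maxima: 18 and 56 for three levels, 24 and 62 for four. The phase I minimum stays at 6.

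**Which paths pass 56**

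If the MTD is level -2 or higher, at most 2 x 6 = 12 patients lie above it, so the total is at most 12 + 44 = 56. Passing 56 therefore needs level -3 to be the MTD. Each of the three higher levels has then failed after 3 or after 6 patients, which gives 2 x 2 x 2 = 8 patterns:

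| Higher levels that failed after six | Patterns | Patients above MTD | Total with both cohorts full |
|---|---|---|---|
| 0 | 1 | 9 | 53 |
| 1 | 3 | 12 | 56 |
| 2 | 3 | 15 | 59 |
| 3 | 1 | 18 | 62 |

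Four of the eight patterns exceed 56, but the patterns are not equally likely. Both cohorts must also reach stage 2. If lymphoma stops at 7, the largest total is 18 + 30 + 7 = 55. If solid tumor stops at 16, it is 18 + 16 + 14 = 48.

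**How likely this is**

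The documents give no DLT rates, so the rates below are assumptions. For a DLT rate p at a level:

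- fails at 3 = P(2 or more DLTs in 3);
- passes = P(at most 1 DLT in the first 3 and at most 1 in all 6);
- fails at 6 = 1 minus the other two.

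For example, at p = 20% these are 0.104, 0.655 and 0.241. The probability that two or three of the higher levels fail at 6, the rest fail at 3, and level -3 passes is then 3 x 0.241² x 0.104 x 0.655 + 0.241³ x 0.655 = about 0.021.

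The chance that both cohorts pass stage 1 at their target rates is P(X > 1 | 16, 0.20) x P(X > 0 | 7, 0.30) = 0.859 x 0.918 = 0.788. At the 5% null rate in both cohorts it is 0.189 x 0.302 = 0.057.

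| Assumed DLT rates, levels 1 / -1 / -2 / -3 | Dose-finding path can exceed 56 | x 0.788 (target rates) | x 0.057 (null rate) |
|---|---|---|---|
| 10% at all | 0.1% | 0.1% | below 0.1% |
| 20% at all | 2.1% | 1.7% | 0.1% |
| 30% at all | 5.6% | 4.4% | 0.3% |
| 50 / 40 / 30 / 15% | 17.0% | 13.4% | 1.0% |

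Phase I alone can pass 18 whatever happens in the Simon stages, and whether or not level -3 is tolerated. Under the same four assumptions the probability is 0.1%, 3.0%, 11.5% and 21.0%.

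**What does not change**

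Recomputed alpha and power are 0.048 and 0.807 for solid tumor, and 0.027 and 0.810 for lymphoma. Neither depends on the dose-finding count.

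**The case against.** The strongest case on the other side concerns weight. The figure of 18 is introduced as an estimate, Table 1 governs accrual in practice, and no boundary, error rate or endpoint depends on either number. Passing 56 takes an unusual run of events. The highest probability above, 13.4%, comes from a curve with a 50% DLT rate at a starting dose that section 2.6 expects to be tolerated. A milder assumed curve of 30/20/15/10% gives 3.0% before the stage 1 factor, and 20/15/10/5% gives 0.7%. All of this stands, and it is why the point is a correction of stated figures and not a design flaw. It does not rescue the figures, because a maximum has to cover every path the rules permit. The sentence with 18 gives its own basis of six per cohort, and the sentence with 56 is not hedged.

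Four levels can total 18 on some paths, such as 3 + 3 + 6 + 6, but that is neither the maximum nor six per cohort.

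A further objection is that 62 is not a ceiling on everyone enrolled, because patients above the MTD need not be evaluable for efficacy and non-evaluable patients are replaced. This is right about total enrolment. But the stated 56 uses the same convention, and on that convention the four-level figure is 62. Replacements come on top of either number.

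**Conclusion.** The concern holds. The phase I maximum is 24, not 18, and the overall evaluable maximum is 62, not 56. Each is understated by 6 patients, and 6/62 is about 10% of the correct overall figure. This rests on the four levels in the Schema, section 3 and Table 5, on Table 1 as written, and on the plan's own convention of counting all phase I patients and reusing the six at the MTD. The phase I overrun needs only the Table 1 rules. The overall overrun, to 59 or 62, is conditional on level -3 being the MTD, at least two higher levels failing only after six patients, and both cohorts reaching stage 2. Its probability depends on DLT rates that the documents do not give: it is small if the regimen is well tolerated and becomes material if toxicity is high at the upper levels.

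**What to change.** Restate three numbers in two places:

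- Schema: phase I range 6-18 becomes 6-24.
- Section 12.1: phase I maximum 18 becomes 24.
- Section 12.1: overall maximum 56 becomes 62 evaluable patients.

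The dose levels, Table 1, the Simon boundaries, alpha and power stay as they are. The cost is the wording change, plus the written amendment and approvals that section 14.6 requires for any change to the protocol.
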